1.3 Secondary Study Endpoints

State the secondary endpoints to be measured in the study.

The secondary endpoint to be measured in the study is the degree to which the CSA module (*Smart Parents – Safe and Healthy Kids*) is implemented with fidelity. We are assessing this in three ways: parent report, provider self-report, and observation through audio recording.

2.0 Background

2.1 Scientific Background and Gaps

Describe the scientific background and gaps in current knowledge.

Child sexual abuse (CSA) is a public health problem in the United States (USDHHS, 2015) and its biopsychosocial consequences are well-documented (e.g., Noll et al., 2007, 2009, 2011). Whereas evidence-based prevention efforts for physical abuse and neglect have achieved the gold standard of reducing rates of those forms of maltreatment (e.g., SafeCare; Self-Brown et al., 2012), CSA primary prevention efforts have not (Letourneau et al., 2014). While adequate school, community, and clinical treatment CSA primary prevention programs exist, evidence-based CSA prevention programs designed for direct delivery to parents do not. Parents are the chief agents of change for children and involving parents in prevention efforts significantly enhances efficacy and uptake (Mendelson & Letourneau, 2015). Targeting high-risk parents for selective prevention is especially important because at-risk parents (i.e., parents involved with child welfare) are likely to (1) experience parenting challenges such as skills (e.g., monitoring) deficits, high stress, little social support, and (2) have their own abuse

histories (Whitaker et al., 2008). This kind of environment places children at greater risk for experiencing sexual abuse, not necessarily by parents themselves, but by other adults or older children. At-risk parents are likely to create environments where children are vulnerable to perpetrators of sexual abuse (Noll, 2008).

In Pennsylvania, many of these at-risk parents are already receiving parent-education services (e.g., The Incredible Years, Parents as Teachers, SafeCare) which teach parents the fundamentals of children’s healthy physical and emotional development, parent-child communication and relationship-building, as well as strategies to ensure children’s physical safety. However, how to create protective environments from perpetrators of sexual abuse is not covered in any of these broader existing parent-education programs. If a brief CSA prevention module was added onto preexisting services where knowledge and skills are already being taught, then a cost-effective, efficacious, widely disseminated CSA primary prevention effort could begin to address this missing prevention piece.

In order to determine if such a prevention effort is effective, it must undergo a randomized controlled trial (RCT) that compares the hypothesized improvement in outcome among participants who receive the program to a group of participants who do not receive the intervention module. RCTs are the most rigorous way of determining whether a cause-effect relationship exists between treatment and outcome (Sibbald & Roland, 1998). An RCT is required to demonstrate that our CSA prevention program produces change in parents’ knowledge, attitudes, and protective behaviors regarding CSA prevention. This change can be demonstrated due to the random allocation of participants to either the intervention or control group because randomization ensures that no between-group systematic differences could explain the cause-effect relationship of the intervention on the outcome. To date there have been no RCTs of a single-session CSA prevention module that has been added onto an existing parent-education program. The proposed study seeks to determine if a single-session CSA prevention module (*Smart Parents – Safe and Healthy Kids*) can improve parents’ knowledge, attitudes, and protective behaviors regarding CSA prevention by being added onto The Incredible Years, Parents as Teachers, and SafeCare.

Implementing an evidence-based intervention necessitates that it is executed the way in which the intervention was originally designed. If an intervention demonstrated a positive effect on behavior, the only way one can be sure they can replicate that positive effect is to deliver the intervention in the exact same way. This process is known as implementing with fidelity. Fidelity monitoring may be done in a variety of approaches including participant report, provider report, or direct observation. Typically, interventions use one form of fidelity monitoring, but empirical studies often cite the importance of utilizing multiple methods of monitoring (Resnicow et al., 1998). Given that we are introducing an additive intervention approach to multiple parent-education models, assessing fidelity of our added module in two different methods is a secondary outcome of interest. We are including multiple methods of fidelity monitoring to assess if one method of fidelity monitoring (e.g., provider self-report, parent report, and direct observation) is sufficient. This has implications for reducing burden/cost in future work.

2.2 Previous Data

Describe any relevant preliminary data.

Data collected during an Acceptability and Feasibility trial (in approved STUDY00006402) in late 2017 informed revisions to the *Smart Parents – Safe and Healthy Kids* module, specifically pacing of the presentation of materials and adjustments for group delivery. Feedback on the content and presentation of the module was universally positive. Providers who observed delivery of the module found it “extremely beneficial to parents of kids of all ages...taught in a very practical, non-threatening way” and thought it “fits very well into the [existing parenting] curriculum.” Parents who received the module reported feeling confident they could use the module and would recommend it to a friend; 100% of participating parents found the module helpful.

2.3 Study Rationale

Provide the scientific rationale for the research.

The *Smart Parents – Safe and Healthy Kids* module is not intended to teach parents basic foundational knowledge about children’s healthy development, parent-child communication, nor how to keep children safe from general harm. Instead, the purpose of the brief behavioral intervention is to teach parents about children’s healthy sexual development, parent-child communication about sexual abuse, and children’s sexual safety. Programs such as Incredible Years, Parents as Teachers, and SafeCare are implemented widely, are evidence-based, and teach parents the aforementioned foundational knowledge and skills and are therefore good candidates for our additive strategy. Additionally, Incredible Years, Parents as Teachers, and SafeCare are delivered to parents via two different approaches: Incredible Years is a group-based delivery whereas Parents as Teachers and SafeCare are home visiting programs (the programs are described in greater detail below). Thus, by adding the CSA module to each of these programs, we will be able to determine the module’s effectiveness across a variety of ages and implementation strategies. No previous research has been conducted on this CSA prevention module, nor has an RCT been conducted on a parent-focused CSA prevention module designed to be added onto existing parent-education programming.

The Incredible Years (IY) is a parent-education program for parents of children aged approximately 0–13. The Incredible Years program aims to increase positive parenting and parent-child bonding, decrease harsh discipline, increase monitoring, and improve parent-child communication. Depending on the age group of the children, 8 to 20 sessions, 2 hours in duration, are delivered to groups of approximately 10 parents. The Incredible Years has been delivered to parents from a variety of populations, including parents involved with child welfare (Webster-Stratton & Reid, 2010). In these studies, The Incredible Years’ intervention effects demonstrated significant improvements in positive parenting compared to individuals who received care as usual. Further accumulated evidence over the course of decades of peer-reviewed research suggests that IY is effective in changing both children and parents’ knowledge and behaviors. For example, improvements in parental attitudes and parent-child interactions have been demonstrated, as well as reductions in harsh discipline and child conduct problems in a series of RCTs (e.g., Reid, Webster-Stratton, & Hammond, 2007; Webster-Stratton, Reid, & Hammond, 2004).

Parents as Teachers (PAT) is a parent-education program which focuses on parent-child interaction, development-centered parenting, and family well-being (Albritton, Klotz, & Roberson, 2003). Families are eligible for PAT until the child enters kindergarten, but as the program works with a family unit the educator may continue to work with the family if there are younger children. Results from several trials suggest that PAT: detects developmental delays and child physical health problems early (Pfannenstiel & Lente-Jojola, 2011); improves children’s language ability, social development and other cognitive abilities (Drotar, Robinson, Jeavons, & Kirchner, 2009; Wagner, Spiker, & Linn, 2002); decreases the achievement gap between low-income and more advantaged children at Kindergarten entry (Pfannenstiel, Seitz, & Zigler, 2003); and improves parents engagement with their child’s schooling (Zigler, Pfannenstiel, & Seitz, 2008). Other findings from PAT research demonstrate improvement in parenting knowledge, attitudes, and behaviors (Pfannenstiel & Seltzer, 1989; Wagner & Clayton, 1999).

SafeCare (SC) is a parent-support program for parents of children 0–5 who are at-risk or have been involved with child welfare services. The program teaches parents skills in three core areas (parenting, home safety, and child health) to reduce the risk for maltreatment. Specifically, parents are taught to positively interact with their children, identify and remove potential safety hazards in the home, and to recognize and respond to children’s illnesses or injuries. The program is delivered over the course of approximately 18 weeks, 6 weeks per module, 3 modules total. Decades of research have established a strong evidence-base for SC (Guastafarro & Lutzker, 2017; 2012). Most notably, in a statewide trial of more than 2,000 families, those that received SafeCare were significantly less likely to have repeat

involvement with child protective services compared to families who received services as usual and these findings remained consistent 7 years post-intervention (Chaffin et al., 2012).

Incredible Years, PAT, and SC are evidence-based parent-education programs that cover a wide range of children's ages (0–13 and 0–5, respectively) and modalities (group-based and home visiting, respectively). All three programs have demonstrated important changes in parenting knowledge, attitudes, and behaviors in high-risk (i.e., child welfare involved) parents. For this reason, IY, PAT, and SC are good candidates onto which *Smart Parents – Safe and Healthy Kids* may be added.

3.0 Inclusion and Exclusion Criteria

Create a numbered list below in sections 3.1 and 3.2 of criteria subjects must meet to be eligible for study enrollment (e.g., age, gender, diagnosis, etc.). Indicate specifically whether you will include any of the following vulnerable populations: (You may not include members of these populations as subjects in your research unless you indicate this in your inclusion criteria.) Review the corresponding checklists to ensure that you have provided the necessary information.

- **Adults unable to consent**
 - Review “CHECKLIST: Cognitively Impaired Adults (HRP-417)” to ensure that you have provided sufficient information. HRP-417 can be accessed by clicking the Library link in CATS IRB (<http://irb.psu.edu>).
- **Individuals who are not yet adults (infants, children, teenagers)**
 - If the research involves persons who have not attained the legal age for consent to treatments or procedures involved in the research (“children”), review the “CHECKLIST: Children (HRP-416)” to ensure that you have provided sufficient information. HRP-416 can be accessed by clicking the Library link in CATS IRB (<http://irb.psu.edu>).
- **Pregnant women**
 - Review “CHECKLIST: Pregnant Women (HRP-412)” to ensure that you have provided sufficient information. HRP-412 can be accessed by clicking the Library link in CATS IRB (<http://irb.psu.edu>).
- **Prisoners**
 - Review “CHECKLIST: Prisoners (HRP-415)” to ensure that you have provided sufficient information. HRP-415 can be accessed by clicking the Library link in CATS IRB (<http://irb.psu.edu>).
- **Neonates of uncertain viability or non-viable neonates**
 - Review “CHECKLIST: Neonates (HRP-413)” or “CHECKLIST: Neonates of Uncertain Viability (HRP-414)” to ensure that you have provide sufficient information. HRP-413 and HRP-414 can be accessed by clicking the Library link in CATS IRB (<http://irb.psu.edu>).

3.1 Inclusion Criteria

List the criteria that define who will be included in your study.

Parents

1. Parent or caregiver \geq 18 years old
2. Parent or caregiver of at least one child under 13
3. Enrolled in either Incredible Years, PAT, or SafeCare parent-training program

Providers

1. 18 years or older

Provider of either Incredible Years, PAT, or SafeCare parent-training program from a site that has agreed to participate in the research and was trained in SPSHK

3.2 Exclusion Criteria

List the criteria that define who will be excluded in your study.

1. Parent/caregiver does not speak English
2. Parent is mandated (i.e., court-ordered) to attend parent-training program

Providers who are not implementing SPSHK.

3.3 Early Withdrawal of Subjects

3.3.1 Criteria for removal from study

Insert subject withdrawal criteria (e.g., safety reasons, failure of subject to adhere to protocol requirements, subject consent withdrawal, disease progression, etc.).

1. Participant decides to withdraw from the parent-training program
2. Participant decides to withdraw at any point from the survey

Providers who decide to not deliver the module.

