3.3.2 Follow-up for withdrawn subjects

Describe when and how to withdraw subjects from the study; the type and timing of the data to be collected for withdrawal of subjects; whether and how subjects are to be replaced; the follow-up for subjects withdrawn from investigational treatment.

If a participant (parent or provider) decides to stop before the study's conclusion, a member of the research team will ask if they wish to have their information used at all; if no, we will purge their information from our database. If the participant indicates that we can use their unidentifiable information, we will retain their available survey data and remove their identifiers from the master list.

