7.2.3 Post-parenting Intervention Assessment

Provide a description as defined above and format accordingly.

Completion of the parenting intervention is specific to each parenting program. For PAT, completion of intervention (for the purposes of our research) is at the end of the fifth foundational visit. For Incredible Years, completion of intervention (for the purposes of our research) is the penultimate session – this is the last session in which content is delivered; the final session is a celebration and graduation. For SafeCare, completion of intervention (for the purposes of our research) is at the conclusion of the parenting module (6 weeks).

Parents will be provided with another paper survey. Those who have not agreed to participate in the research will be allowed to leave. Participants will complete the APQ and Module Assessment (‘Measure_ParentAssessmentTool’ in supporting documents).

7.2.4 One-week Post-parenting (control) OR Post-parenting and Module Assessment (Experimental group)

Provide a description as defined above and format accordingly.

One-week after completing the parenting program (7.2.3), parents in the control condition that have agreed to participate in the research will be contacted by the research team to complete the third assessment, the APQ, Module Assessment ('Measure_ParentAssessmentTool'). {This will happen within a normally scheduled session of PAT or SafeCare, and will require an additional visit for the IY participants}

The week after the conclusion of event 7.2.3, providers in the experimental condition deliver the Smart Parents – Safe and Healthy Kids module to their parents. The parent and provider will complete a short survey about the content of the session. This is done each time the module is delivered to measure fidelity. Additionally, provider-participants will record any two SPSHK sessions where the participating parent(s) agree to the recording. If the parent in the individual session—or any parent in the group session—declines to be audio recorded, the SPSHK module will be delivered as usual (including the fidelity survey), but the session will not be audio recorded.

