7.2.5 One-month Follow-up Assessment

Provide a description as defined above and format accordingly.

One month after 7.2.4, when intervention is complete -- the post-parenting intervention assessment for the control group and the post-module assessment for the experimental group, a member of the research team will follow up with participants using the preferred method of contact they indicated in 7.2.1 and distribute the final survey packet over email (link to an electronic version of the survey) or a hard copy through the mail with a prepaid envelope for return to Penn State. They will complete the Module Assessment and APQ.

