7.3 Duration of Participation

Describe the duration of an individual subject's participation in the study.

Duration of participation for Incredible Years participants that is approximately 15 weeks (depending on mastery of the material), for Parents as Teachers participants that is approximately 6 weeks (depending on mastery of the material), and for SafeCare participants that is approximately 7 weeks (depending on mastery of the material). The control condition lasts the length of the parenting program in which they are participating (14 weeks for IY, depending on mastery of the material; 5 weeks for PAT, depending on mastery of the material; 6 weeks for SafeCare, depending on mastery of the material). The one week of

follow up is outside the provision of the program. Total participation extends one month beyond that to include the final follow-up assessment.

The estimated total time for a participant in the experimental condition to complete all assessments is 60 minutes; the estimated total time for a participant in the control condition to complete all assessments is 55 minutes.

Providers participation in fidelity research (i.e., self-report will be approximately 5 minutes in all sessions they deliver the SPSHK module.

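### Leaving the parenting programme removes a parent from the study, so one who leaves before the module without refusing surveys has no stated route to the one-month survey

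*Combined protocol and SAP*

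**What the plan says.** Section 3.3.1 gives two removal criteria for parents. The first is "Participant decides to withdraw from the parent-training program". The second, on its own line, is a decision to stop the survey. Neither carries a time limit.

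Section 3.3.2 says that the team will ask a participant who stops early whether their information may be used. If not, it is purged. If so, "we will retain their available survey data and remove their identifiers from the master list". No later assessment is described, although the template prompt above the answer asks about follow-up of subjects who leave the treatment.

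For T4, section 7.2.5 has the research team "distribute the final survey packet over email (link to an electronic version of the survey) or a hard copy through the mail". No programme session is involved.

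The programme's length is described in two ways. In section 2.3, SafeCare is the full course ("The program is delivered over the course of approximately 18 weeks, 6 weeks per module, 3 modules total") and PAT is open-ended ("Families are eligible for PAT until the child enters kindergarten"). Section 7.2.3 sets completion for research purposes at six weeks in SafeCare, the fifth visit in PAT and the penultimate Incredible Years session. Section 7.3 then gives the programme as about 14, 5 and 6 weeks for Incredible Years, PAT and SafeCare, and adds: "Total participation extends one month beyond that to include the final follow-up assessment".

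Section 2.1 rests the causal claim on randomisation: "This change can be demonstrated due to the random allocation of participants to either the intervention or control group". Section 7.1 places that randomisation at site level. Section 8.3 leaves the model open and names neither an analysis set nor a method for missing data.

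**The concern.** Leaving a parenting programme happens after randomisation, and the rate of leaving may differ between the arms. If leaving ends data collection, the one-month outcome is known only for parents who stayed, and the two groups of stayers need no longer be comparable.

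T2 and T3 are largely tied to sessions, so a parent who leaves may miss them whatever the protocol says. T4 is different: it reaches the parent by e-mail or post, and the study already collects contact sheets to prevent loss to follow-up (section 9.1.1). Losing T4 from a parent who would have answered it is avoidable.

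**Working it through.** **1. Who is caught.** Because stopping the survey has its own line in 3.3.1, the first criterion also reaches parents who are still willing to answer. Section 3.3.2 deals only with data already held. A parent who leaves before the module therefore meets 3.3.1, and no section provides for their T4. This holds in all three trials and on either meaning of the programme.

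**2. After the module.** Timing from sections 2.3, 7.2.3, 7.2.4 and 7.3, taking one month as about 4 weeks:

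| Trial | Research completion | Module / T3 | T4 | Whole programme |
|---|---|---|---|---|
| SafeCare | week 6 | week 7 | 7 + 4 = week 11 | about 18 weeks |
| PAT | week 5 | week 6 | 6 + 4 = week 10 | to kindergarten |
| Incredible Years | penultimate session | week after | one month later | content already finished |

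If the criterion means the whole programme, a SafeCare parent leaving between weeks 7 and 11, or a PAT parent between weeks 6 and 10, meets it after receiving the module. If it means the research segment, that parent has already completed the programme and does not. Incredible Years has essentially no such window.

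**3. The plan's own figure.** Repeated-measures ANOVA, between factors: d = .45, 4 assessments, two-sided alpha .05, correlation .7. The .7 is stated only for Incredible Years and is assumed here for PAT and SafeCare. The variance factor is (1 + 3 × .7)/4 = .775, and 62 per arm gives power .806. This reproduces the stated 62.

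**4. Selection and dilution.** Let pE and pC be the proportions leaving in the experimental and control arms. Let leavers score g SD below stayers, apart from any module effect. All values of p and g are assumed.

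- Leavers get the same module effect as stayers: stayers-only minus all-by-arm = (pE − pC) × g.
- Leavers get no module: stayers-only minus all-by-arm = (pE − pC) × g + pE × .45.

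The first term is selection. The second is dilution, which is a change in the quantity estimated.

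- Selection, low end: .05 × .3 = .015 SD. High end: .15 × .5 = .075 SD. Either sign is possible.
- Equal leaving: selection is 0.
- 30% experimental, 15% control, g = .5: .075 + .135 = .21, of which .135 is dilution.
- 10% experimental, 25% control, g = .5: −.075 + .045 = −.03.

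For scale, the standard error in PAT or SafeCare is √(2 × .775/62) ≈ .16 SD.

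**5. T4 surveys at stake.** At an assumed 10%, 20% or 30% leaving: 62 × p = 6.2, 12.4 or 18.6 per arm in PAT or SafeCare; 140 × p = 14, 28 or 42 per arm in Incredible Years. The Incredible Years number already allows for attrition and non-participation (11 raised to 14 groups, 1 − 11/14 = 21%). Section 8.2 states no allowance for PAT or SafeCare.

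**6. Power, PAT or SafeCare, at the same leaving rates.**

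| Leaving | Complete cases, d = .45 | All parents followed, d = .45 × (1 − p) | Half of leavers reply |
|---|---|---|---|
| 10% | .76 | .72 (d = .405) | .74 |
| 20% | .71 | .62 (d = .36) | .66 |
| 30% | .65 | .51 (d = .315) | .57 |

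The last two columns assume that all leaving precedes the module. All columns treat parents as independent despite site randomisation, and count each parent as wholly in or wholly out.

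**The case against.** Section 3.3.2 can be read as being about stopping the study, not the programme. It does not forbid later surveys, and section 9.1.1.1 keeps contact details of enrolled participants until the study ends. That is fair: this is silence, not a prohibition. But 3.3.1 classes the programme leaver as removed, and the general rule on contact details creates no follow-up for removed parents.

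Section 1.1 frames the hypothesis around parents who receive the module, so those who leave earlier fall outside it. A completers' comparison may be of interest, but that group is formed after randomisation and cannot carry the causal claim in section 2.1.

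Three stronger readings are tempting, and the documents do not support them.

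- A reader might infer that PAT and SafeCare parents lose T4 even after receiving the module. Sections 2.3 and 3.1 point that way, as does the control-group T3 held in an ordinary PAT or SafeCare session (section 7.2.4). But sections 7.2.4 and 7.3 also use the term for the 5- or 6-week segment, and 7.3 places the week after it outside the programme. The text is ambiguous.
- A reader might infer that the plan analyses stayers only. It does not say so. Surveys already completed are kept unless the parent asks for a purge, and the hierarchical models named in 8.3 can use partial records.
- A reader might quote .21 SD, or .45 against .315, as bias. Most of the first and all of the second is dilution.

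The Incredible Years allowance would absorb losses of 14 or 28 per arm in number. It protects sample size, not comparability.

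**Conclusion.** The point holds for parents in any of the three trials who leave before the module without refusing surveys: they have no stated route to T4, though collecting it needs no attendance. For PAT and SafeCare parents who leave after the module, the finding is only that 3.3.1 must say whether it applies.

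The consequence is a possible selection bias of unknown size and direction, because the documents give neither leaving rates nor leaver-stayer differences. The illustrative .015 to .075 SD is under half a standard error in one PAT or SafeCare trial, and it is zero if leaving is equal by arm and the effect is the same in leavers and stayers. This is a cheap improvement, not a fatal flaw.

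**What to change.** - In 3.3, separate stopping the parenting programme from withdrawing from the research. Purge or de-link only for the second.
- For the first group, keep contact details and seek the remaining surveys, at least T4, by the existing e-mail or mail route. Send T4 one month after T3 if T3 was done, otherwise one month after the parent's expected T3 date at that site. Fixed calendar weeks would not suit durations that depend on mastery (sections 7.2.2 and 7.3).
- State in 3.3.1 that leaving PAT or SafeCare after the module does not remove a parent from T4.
- In 8.3, analyse all consented parents by their site's assigned arm with all available assessments, for example in a mixed model, and report programme completers as supplementary.

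Besides the wording, contact details are held longer and each extra T4 costs $20 (section 14.0). With full reply at 10%, 20% or 30% leaving, that is 124 × p × $20 = $248, $496 or $744 per PAT or SafeCare trial, and 280 × p × $20 = $560, $1,120 or $1,680 for Incredible Years.

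The estimate will be diluted by experimental parents who leave before the module, and power falls as tabulated above. The gain is freedom from this selection, to the extent that leavers reply.
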